9.1. Sample Size Determination

The study size is not based on any formal statistical hypothesis test. Approximately 188 infants per vaccine group are planned to be randomized. No hypothesis tests between vaccine groups are planned; therefore, no power calculations for comparison of vaccine groups are included.

With 188 subjects per arm, the probabilities of observing at least 1 AE, local reaction, or systemic event where the true rate is 0.5%, 1%, and $\geq 5\%$ are presented in Table 5.

Table 5. Probability of Observing at Least 1 AE, Local Reaction, or Systemic Event by Assumed True Event Rates

Sample Size	Assumed True Event Rate of at Least 1 AE, Local Reaction, or Systemic Event		
	0.5%	1%	≥5%
N = 188	0.610	0.849	>0.999

9.2. Analysis Populations

The safety population will include all Group 1 and Group 2 subjects who receive at least 1 dose of c7vPnC and all Group 3 subjects who receive at least 1 dose of Prevnar 13. Subjects will be assigned to vaccine groups corresponding to the vaccine series actually received. The safety population will be the only analysis population for the primary endpoints.

The Dose 3 evaluable immunogenicity population will include any subject:

1. Who was eligible for the study.

- 2. Who was randomized and met the SAP-specified age window on the first day of vaccination for the randomized group (age windows will be same for Groups 1 and 3, but different for Group 2).
- 3. Who received c7vPnC and/or Prevnar 13, as randomly assigned, through Dose 3.
- 4. Who had an IgG concentration for at least 1 serotype 1 month after Dose 3.
- 5. Whose blood collection was within the SAP-specified window after Dose 3.
- 6. Who had no other major protocol deviations as determined by the clinician or medical monitor.

Additional criteria may be described in the SAP. The Dose 3 evaluable immunogenicity population will be the primary analysis population for immunogenicity results from the blood collected 1 month after Dose 3.

The Dose 4 evaluable immunogenicity population will include any subject:

- 1. Who was eligible for the study.
- 2. Who was randomized and met the SAP-specified age window on first day of vaccination for the randomized group (age windows will be same for Groups 1 and 3, but different for Group 2).
- 3. Who received the assigned vaccine, as randomized, within the defined window for Dose 4 as specified in the SAP.
- 4. Who received the vaccine to which he or she was randomly assigned at all 4 doses.
- 5. Who had an IgG concentration for at least 1 serotype 1 month after Dose 4.
- 6. Whose blood collection was within the SAP-specified window after Dose 4.
- 7. Who had no other major protocol deviations as determined by the clinician or medical monitor.

Additional criteria are described in the SAP. The Dose 4 evaluable immunogenicity population will be the primary analysis population for immunogenicity results after Dose 4.

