2.1.2. Primary Endpoints

- Proportions of subjects reporting prompted local reactions (redness, swelling, and pain at the injection site) within 7 days of each dose.
- Proportions of subjects reporting prompted systemic events (fever, decreased appetite, drowsiness/increased sleep, and irritability) within 7 days of each dose.
- Proportions of subjects reporting adverse events (AEs) from Dose 1 to 1 month following Dose 3 and from Dose 4 to 1 month following Dose 4/Supplemental Dose.

• Proportions of subjects reporting serious adverse events (SAEs) and newly diagnosed chronic medical conditions (NDCMCs) from Dose 1 to 6 months following Dose 4/Supplemental Dose.

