Subjects will be observed for 30 minutes after each dose of c7vPnC in Groups 1 and 2, and after Prevnar 13 and the Supplemental Dose of c7vPnC in Group 3. In all groups, prompted local reactions (pain, redness, and swelling at the injection site), systemic events (fever, decreased appetite, drowsiness/increased sleep, and irritability), and use of antipyretic/pain medications occurring within 7 days after Doses 1 to 4 and the Supplemental Dose will be collected each day in the electronic diary (e-diary). SAEs and NDCMCs will be collected for the entire duration of the study. AEs (including nonserious AEs, SAEs, and NDCMCs) will be collected from the signing of the informed consent document to 1 month after Dose 3 and from Dose 4 to 1 month after Dose 4 or 1 month after the Supplemental Dose in Group 3. Approximately 6 months after Dose 4 or the Supplemental Dose, the sites will contact the subject's legally acceptable representative via telephone to inquire about SAEs and NDCMCs. Blood will be drawn for immunogenicity assessments 1 month after Dose 3, prior to receipt of Dose 4, and 1 month after Dose 4

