6.2. Group 2 (Staggered Administration) Study Procedures

6.2.1. Group 2 Visit 1 (Prevnar 13: 2-Month Visit, Day 1)

Prior to randomization:

- A personally signed and dated informed consent document indicating that the subject's legally acceptable representative has been informed of all pertinent aspects of the study before performing any study-specific procedures.
- Record the subject's demographic information (including date of birth, sex, race, and ethnicity).
- Obtain and record the subject's medical history including prior vaccinations.
- Perform physical examination evaluating any clinically significant abnormalities within the following body systems: general appearance; skin; head, eyes, ears, nose, and throat; heart; lungs; abdomen; musculoskeletal; extremities; neurological; and lymph nodes. Clinically significant abnormal results will be recorded in the CRF.
- Ensure that all inclusion criteria and none of the exclusion criteria are met.

• Assign randomization number and investigational product container number via the IRT. This must be the last step before proceeding. A site staff member will prepare the investigational product according to the IP manual.

After randomization:

- Administer a single 0.5-mL injection of Prevnar 13 into the right anterolateral thigh.
- Administer DTaP-containing vaccine and other permitted vaccines (to be administered into a limb other than the left leg).
- Ask the subject's legally acceptable representative to contact the investigator or investigator site staff as soon as possible if any significant illness or medical event (eg, emergency room visit or hospitalization) occurs.
- Inform the subject's legally acceptable representative that use of prophylactic antipyretic/pain medication, while permitted, is not recommended on the day of investigational product administration (before or after vaccination).
- The investigator or an authorized designee completes the CRF and updates the investigational product accountability records.

6.2.2. Group 2 Visit 2 (c7vPnC Dose 1: 3-Month Visit, 21 to 35 Days After Prevnar 13 at Visit 1)

- Ensure and document that the subject continues to be eligible for the study (see Section 6.5 for withdrawal information), and none of the temporary delay criteria are met.
- Record vaccines administered since Visit 1 as described in Section 5.7.4.

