- Determine whether any AEs (includes nonserious AEs, SAEs, and NDCMCs) have occurred since the previous visit and follow up on any previously reported events to determine the outcome (ie, record stop dates or confirm if they are still continuing) and record as described in Section 8, and record concomitant medications used to treat SAEs and NDCMCs.
- Measure and record the subject's rectal temperature (${}^{\circ}F/{}^{\circ}C$).
- Administer a single 0.5-mL injection of c7vPnC into the left anterolateral thigh.

After vaccination:

• Site staff will observe the subject for at least 30 minutes after vaccination for any acute reactions. Record any AEs on the CRF and on an SAE form as applicable. Record concomitant medications used to treat SAEs and NDCMCs.

- Issue the subject's legally acceptable representative a measuring device to measure injection site reactions and a digital thermometer and provide instructions on their use.
- Issue the subject's legally acceptable representative an e-diary (device or application). Provide instructions on use and completion of the e-diary. Ask the subject's legally acceptable representative to complete the e-diary from Day 1 to Day 7, with Day 1 being the day of vaccination.
- Ask the subject's legally acceptable representative to contact the investigator site staff or investigator as soon as possible during the 7-day postvaccination period if the subject has a fever >104.0°F (>40.0°C), redness and/or swelling at the injection site measuring >14 measuring device units (>7 cm), or severe injection site pain (causes limitation of limb movement) to determine if the event requires further assessment by the investigator.
- Ask the subject's legally acceptable representative to contact the investigator or investigator site staff as soon as possible if any significant illness or medical event (eg, emergency room visit or hospitalization) occurs during the study period.
- Remind the subject's legally acceptable representative that use of prophylactic antipyretic/pain medication, while permitted, is not recommended on the day of investigational product administration (before or after vaccination).
- The investigator or an authorized designee completes the CRF and updates the investigational product accountability records.

6.2.3. Group 2 Visit 3 (Prevnar 13: 4-Month Visit, 42 to 63 Days After Prevnar 13 at Visit 1)

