8.1.4. Time Period for Collecting AE/SAE/NDCMC Information

The time period for actively eliciting and collecting AEs, SAEs, and NDCMCs ("active collection period") for each subject begins from the time the subject's legally acceptable representative provides informed consent, which is obtained before the subject's participation in the study (ie, before undergoing any study-related procedure and/or receiving

investigational product). AEs will be collected through 1 month after Dose 3 and from Dose 4 through 1 month after Dose 4 or 1 month after the Supplemental Dose in Group 3. NDCMCs and SAEs will be collected from signing of informed consent through 6 months after Dose 4 or the Supplemental Dose. An NDCMC is defined as a disease or medical condition, not previously identified, that is expected to be persistent or is otherwise long-lasting in its effects.

For subjects who are screen failures, the active collection period ends when screen failure status is determined.

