9.4. Safety Analysis

All safety analyses will be performed using the safety population.

Descriptive statistics for local reactions for the c7vPnC injection site in Groups 1 and 2 and the Supplemental Dose in Group 3, as well as the Prevnar 13 site in Group 3, and systemic events from Day 1 to Day 7 will be presented by severity and cumulatively across severity levels. Descriptive statistics will include proportions of subjects with the indicated endpoint and the associated Clopper-Pearson 95% CIs. Local reactions will be compiled for each dose for each group (Doses 1, 2, 3, and 4 and the Supplemental Dose) separately and compiled across all 4 doses of the same group.

AEs (including nonserious AEs, SAEs, and NDCMCs) will be compiled over 2 intervals: from Dose 1 to 1 month following Dose 3 and from Dose 4 to 1 month following Dose 4/Supplemental Dose. SAEs and NDCMCs will be summarized from Dose 1 until 6 months after Dose 4/Supplemental Dose. The descriptive statistics for AEs will be summarized as the number and percentage of subjects reporting at least 1 event of each preferred term with the associated Clopper-Pearson 95% CIs, arranged by system organ class.

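### Group 2 events between the first Prevnar 13 visit and the first c7vPnC dose are collected but enter no stated safety table, and Group 2 infants who never receive c7vPnC belong to no stated safety population

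*Protocol*

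**What the plan says.** **Population.** Protocol 9.2: "The safety population will include all Group 1 and Group 2 subjects who receive at least 1 dose of c7vPnC". Group 3 infants enter with one dose of Prevnar 13. The section adds an as-received rule, "Subjects will be assigned to vaccine groups corresponding to the vaccine series actually received", and makes this the only population for the primary endpoints. SAP 4.1 repeats the c7vPnC condition for Groups 1 and 2. Its other safety populations require Dose 1, Dose 4 or the Supplemental Dose.

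**Meaning of Dose 1.** Under Protocol 3, numbered doses are c7vPnC doses in Groups 1 and 2 and Prevnar 13 doses in Group 3. Groups 1 and 3 receive Dose 1 at Visit 1. Group 2 receives Prevnar 13 and a DTaP-containing vaccine at Visit 1, and Dose 1 one visit later: "Group 2 Visit 2 (c7vPnC Dose 1: 3-Month Visit, 21 to 35 Days After Prevnar 13 at Visit 1".

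**Collection.** AEs "will be collected from the signing of the informed consent document to 1 month after Dose 3" (Protocol 3). Protocol 8.1.4 says that "NDCMCs and SAEs will be collected from signing of informed consent through 6 months after Dose 4 or the Supplemental Dose". At Group 2 Visit 2, before the first c7vPnC injection, site staff must "Determine whether any AEs (includes nonserious AEs, SAEs, and NDCMCs) have occurred since the previous visit".

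**Analysis.** Protocol 2.1.2 gives the AE endpoint as "Proportions of subjects reporting adverse events (AEs) from Dose 1 to 1 month following Dose 3 and from Dose 4" (the second period closes a month past the final study vaccination). Protocol 9.4 says that "SAEs and NDCMCs will be summarized from Dose 1 until 6 months after Dose 4/Supplemental Dose". SAP 6.1.3.1 and 6.1.4.1 also start at Dose 1.

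**The concern.** The collection start and the analysis start coincide, apart from any time between consent and vaccination, in Groups 1 and 3. In Group 2 they are 21 to 35 days apart. Two of the four primary endpoints (AEs; SAEs and NDCMCs) therefore leave out collected, post-randomization events in one arm only. A serious event two weeks after the 2-month vaccinations would count in the SAE table for Group 1 or 3 but would appear in no stated SAE table for Group 2.

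A Group 2 infant who leaves after Visit 1 is missing altogether. The as-received rule does not say whether that infant stays in Group 2, moves to Group 3 or is dropped. The SAP's rule on deviating doses applies only to infants already inside a safety population.

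The disposition tables do not fully make up for this. SAP 6.5.1.1 counts randomized infants who withdraw but, read literally, gives reasons for withdrawal (adverse event among them) only from Dose 1. SAP 6.5.3 plans a summary before Dose 1 for vaccines received; no such summary of events is visible.

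**Working it through.** **Inputs.** Approximately 188 infants per group, and Table 5 (Protocol 9.1). Visit windows from the Schedule of Activities: 42 to 63 days between successive Prevnar 13 doses in the infant series; 21 to 35 days from each Prevnar 13 dose to the following c7vPnC dose in Group 2; 28 to 42 days from Dose 3 to the follow-up visit. Dropout of 15% by Dose 3 (Protocol 3.3). The documents give no figure for loss before Group 2 Visit 2.

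**Check of the gap.** SAP 4.2 allows an age of 63 to 133 days at Group 2 Dose 1. The entry age of 42 to 98 days plus the gap gives 42 + 21 = 63 and 98 + 35 = 133, so 21 to 35 days is confirmed.

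**Size of the uncounted window.**
- 188 × 21 = 3,948 and 188 × 35 = 6,580 infant-days. Divided by 365.25, this is 10.8 to 18.0 infant-years.
- Group 2, Visit 1 to 1 month after Dose 3: 42 + 42 + 21 + 28 = 133 to 63 + 63 + 35 + 42 = 203 days; mid-window 168.
- Uncounted share: 28/168 = 16.7% at mid-window; 21/203 = 10.3% and 35/133 = 26.3% at the extremes.

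**Length of the first interval as planned.**
- Groups 1 and 3: 42 + 42 + 28 = 112 to 63 + 63 + 42 = 168 days; mid-window 140.
- Group 2 from Dose 1: (42 + 42 + 21) − 35 + 28 = 98 to (63 + 63 + 35) − 21 + 42 = 182 days; mid-window 140.

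Counted time is thus nominally equal across groups. What differs is whether the 2-month vaccinations fall inside it.

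**Infants excluded (assumption).** If 0.5% to 4.8% of Group 2 are lost between Visits 1 and 2, that is 188 × 0.005 = 0.9 to 188 × 0.048 = 9.0, about 1 to 9 infants. Spreading the 15% dropout evenly over five months gives 188 × (1 − 0.85^(1/5)) = 6.0.

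**Effect on detection.** Table 5 at a 0.5% rate is reproduced: 1 − 0.995^188 = 0.610. With 187 infants it is 0.608, and with 179 it is 0.592. The smaller denominator matters little.

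**7-day diary.** The earliest Visit 3 minus the latest Dose 1 is 42 − 35 = 7 days, so Visit 3 falls on Day 8 or later, after the Day 1 to Day 7 diary. The prompted-event tables are not affected.

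**The case against.** The anchor is deliberate. The primary objective is the safety of c7vPnC, an explicit note ties the numbered doses to c7vPnC in Groups 1 and 2, and an event before any c7vPnC cannot be a reaction to it. Group 2's Prevnar 13 visits have no 30-minute observation and no diary, so Group 3's Dose 1 is not a like-for-like comparison. The study is descriptive, and counted time is already balanced. Protocol 8 sends all SAEs to the sponsor whichever table they enter. SAP 3.1 and 5.3 are partly redacted, and the SAP contents list shows redacted entries after the AE and SAE primary analyses; a rule could sit there.

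Most of this stands, and it is why the Dose 1-anchored tables should remain. It does not close the gap. The anchor does not isolate c7vPnC: Group 2's interval already counts events after the 4- and 6-month Prevnar 13 and DTaP visits and omits only the 2-month one. Nor is the collection incidental. At Visit 2 all AEs are elicited, whereas at Visit 9, after the 12-month Prevnar 13, only SAEs and NDCMCs are.

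A reader might infer more than the documents support:
- **That the safety comparison is biased.** Equal nominal time and unknown event rates in the window give no direction.
- **That the safety population must be widened.** It is the only population for the primary endpoints, so widening it would conflict with keeping c7vPnC recipients as their denominator.
- **That a full regimen-level AE table could be built.** Nonserious AEs are not collected in Group 2 between the 12-month Prevnar 13 dose and Dose 4.

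**Conclusion.** On the visible text the gap is real and confined to Group 2. Events over 21 to 35 days after the first study vaccination are collected and then assigned to no stated interval, for all of the approximately 188 infants. An infant given Prevnar 13 but never c7vPnC meets no stated safety population. The main consequence is unreported events; the loss of denominator is probably small, and the 1 to 9 infants above rest on an assumed loss rate. The infant-day figures assume that all 188 are followed through the visit window; early withdrawals would shorten them, and a temporary delay of Dose 1 could lengthen them. The conclusion also depends on redacted SAP text holding no rule for this period. It is a cheap improvement to the reporting plan and does not challenge the primary analysis.

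**What to change.** Leave the safety population and the Dose 1-anchored primary tables unchanged. Then:

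1. Add to SAP 6.1.3 and 6.1.4 a supplementary Group 2 tabulation in all Group 2 infants who received any study vaccine (Prevnar 13 or c7vPnC), showing (i) AEs, SAEs and NDCMCs from Visit 1 to before Dose 1, and (ii) SAEs and NDCMCs from Visit 1 to the end of follow-up. Show follow-up time with both.
2. State that Prevnar 13-only Group 2 infants stay in Group 2 for these tables and that the as-received rule does not move them to Group 3.
3. In SAP 6.5.1.1, tabulate withdrawal reasons from randomization instead of from Dose 1.

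If redacted text already covers this period, a cross-reference is enough.

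The cost is SAP wording and one or two tables, with no new visits, samples or data. The added intervals are not directly comparable with the other groups and should be labelled so. Follow-up of Prevnar 13-only infants may be incomplete: Protocol 6.2.11 words the 6-month call for infants with at least one c7vPnC dose, although Protocol 6.5 asks for a safety call after withdrawal following investigational product.

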9.3. Immunogenicity Analysis

All serotypes will be analyzed in the same way. All endpoints will be summarized by vaccine group.

9.3.1. Analyses of Secondary CCI Endpoints

The secondary CCl endpoints will be summarized by:

1. Geometric mean concentrations (GMCs) after Dose 3,

CCI

- 3. GMCs after Dose 4,
- 4. Proportions of subjects with IgG concentrations ≥ reference concentration after Dose 3,

Ninety-five percent confidence intervals (CIs) will also be calculated for all descriptive statistics.

GMCs and their CIs will be obtained by taking log transforms of concentrations, calculating the 95% CI with reference to the t-distribution, then exponentiating the mean and the limits. The Luminex assay IgG concentration of 0.35 μ g/mL will be used as the predefined IgG reference concentration for all serotypes, with the exception of serotypes 5 (0.23 μ g/mL), 6B (0.1 μ g/mL), and 19A (0.12 μ g/mL). The 95% CIs will be obtained using the Clopper-Pearson method.⁷⁰

[figure not shown]
9.4. Safety Analysis

All safety analyses will be performed using the safety population.

Descriptive statistics for local reactions for the c7vPnC injection site in Groups 1 and 2 and the Supplemental Dose in Group 3, as well as the Prevnar 13 site in Group 3, and systemic events from Day 1 to Day 7 will be presented by severity and cumulatively across severity levels. Descriptive statistics will include proportions of subjects with the indicated endpoint and the associated Clopper-Pearson 95% CIs. Local reactions will be compiled for each dose for each group (Doses 1, 2, 3, and 4 and the Supplemental Dose) separately and compiled across all 4 doses of the same group.

AEs (including nonserious AEs, SAEs, and NDCMCs) will be compiled over 2 intervals: from Dose 1 to 1 month following Dose 3 and from Dose 4 to 1 month following Dose 4/Supplemental Dose. SAEs and NDCMCs will be summarized from Dose 1 until 6 months after Dose 4/Supplemental Dose. The descriptive statistics for AEs will be summarized as the number and percentage of subjects reporting at least 1 event of each preferred term with the associated Clopper-Pearson 95% CIs, arranged by system organ class.

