- Issue the subject's legally acceptable representative an e-diary (if device needed). Provide and review instructions on use and completion of the e-diary. Ask the subject's legally acceptable representative to complete the e-diary from Day 1 to Day 7, with Day 1 being the day of vaccination. Provide thermometer or measuring device if needed.
- Ask the subject's legally acceptable representative to contact the investigator site staff or investigator immediately during the 7-day postvaccination period if the subject experiences fever >104.0°F (>40.0°C), redness or swelling at the injection site measuring >14 measuring device units (>7 cm), or severe injection site pain (causes limitation of limb movement) to determine if the event requires further assessment by the investigator.
- Remind the subject's legally acceptable representative to contact the investigator or investigator site staff as soon as possible if any significant illness or medical event (eg, emergency room visit or hospitalization) occurs.
- Remind the subject's legally acceptable representative that use of prophylactic antipyretic/pain medication, while permitted, is not recommended on the day of investigational product administration (before or after vaccination).
- The investigator or an authorized designee completes the CRF and updates the investigational product accountability records.

6.1.6. Group 1 Visit 6 (Follow-up: 13-Month Visit, 28 to 42 Days After Dose 4)

- Ensure and document that the subject continues to be eligible for the study (see Section 6.5 for withdrawal information), and none of the temporary delay criteria are met.
- Record vaccines administered since Visit 5 as described in Section 5.7.4.
- Review the subject's e-diary data with the subject's legally acceptable representative; collect stop dates of any e-diary events ongoing on the last day that the e-diary was completed and record stop dates in the CRF.
- Collect the e-diary (if device provided).
- Determine whether any AEs (includes nonserious AEs, SAEs, or NDCMCs) have occurred since the previous visit and follow up on any previously reported events to determine the outcome (ie, record stop dates or confirm if they are still continuing) and record as described in Section 8, and record concomitant medications used to treat SAEs and NDCMCs.

- Collect a blood sample of approximately 5 mL for immunogenicity assessments (a topical anesthetic is permitted).

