4.1. Safety Analysis Population

The **overall safety population** will include all subjects who receive at least 1 dose of c7vPnC (in Groups 1 and 2) or Prevnar 13 (in Group 3) and have safety data reported in the study. Subjects will be reported according to the vaccine actually received. The safety population will be the analysis population for safety and reactogenicity endpoints.

Additional safety populations will be defined as follows:

Dose 1 to Dose 3 Safety Population - Subjects receiving Dose 1 and having safety data between Dose 1 and the visit 1 month after Dose 3.

Dose 4 Safety Population - Subjects receiving Dose 4 and having safety data between Dose 4 and 1 month after Dose 4 for Groups 1 and 2 and having safety data between Dose 4 and Supplemental Dose for Group 3.

Supplemental Dose Safety Population - Subjects receiving Supplemental Dose and having safety data between Supplemental Dose and 1 month after Supplemental Dose.

If a subject's actual vaccine dose deviates from the planned vaccination within a particular safety population (eg, overall or Dose 1 to Dose 3), the subject data will be either analyzed for any by-dose presentation, or data will be presented in listings as appropriate according to the vaccine dose actually received.

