6.1.3. Adverse Events

6.1.3.1. Primary Analysis

Endpoint: Proportions of subjects reporting AEs from Dose 1 to 1 month following Dose 3, from Dose 4 to 1 month following Dose 4, and from Supplemental Dose to 1 month following Supplemental Dose

- Analysis time points: Dose 1 to 1 month after Dose 3, and from Dose 4 to 1 month after Dose 4/Supplemental Dose
- Analysis population: Dose 1 to Dose 3 safety population, Dose 4 safety population, Supplemental dose safety population for supplemental Dose
- Analysis methodology: Descriptive statistics
- Supporting objective: Primary Objective

Reporting results:

The percentage (%), number of subjects and the denominator (N) used in the percentage calculation, and corresponding 95% Clopper-Pearson CI will be presented for each vaccine group.

Figures: None

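### The booster-phase AE proportion, a primary endpoint, has two conflicting definitions for Group 3; the combined one covers 56-84 days against 28-42 days in Groups 1 and 2.

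*Protocol*

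**What the plan says.** **Combined definition.** Protocol 2.1.2 lists, as one of four primary endpoints, the proportion of infants with AEs "from Dose 1 to 1 month following Dose 3 and from Dose 4 to 1 month following Dose 4/Supplemental Dose". Protocol 9.4 confirms that there are only two intervals: AEs are "compiled over 2 intervals: from Dose 1 to 1 month following Dose 3 and from Dose 4 to 1 month following Dose 4/Supplemental Dose". Protocol 3 shows how to read the slash, because AE collection runs "from Dose 4 to 1 month after Dose 4 or 1 month after the Supplemental Dose in Group 3"; Protocol 8.1.4 says the same. SAP 3.1 repeats the endpoint, and SAP 6.1.3.1 has the bullet "Analysis time points: Dose 1 to 1 month after Dose 3, and from Dose 4 to 1 month after Dose 4/Supplemental Dose".

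**Split definition.** The endpoint line of that same SAP section ends differently: "from Dose 4 to 1 month following Dose 4, and from Supplemental Dose to 1 month following Supplemental Dose". Its population bullet names three sets (Dose 1 to Dose 3, Dose 4, Supplemental Dose). SAP 4.1 defines the Dose 4 safety population by data up to one month after Dose 4 in Groups 1 and 2, but by "having safety data between Dose 4 and Supplemental Dose for Group 3", and gives the Supplemental Dose a population of its own.

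**Visit windows.** Group 1 is seen 28-42 days after Dose 4 (Protocol 6.1.6), and so is Group 2 (Protocol 6.2.10). Group 3 receives the Supplemental Dose at its Visit 6, 28-42 days after Dose 4 (Protocol 6.3.6), and returns 28-42 days after that (Protocol 6.3.7).

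**The concern.** Group 3 is the only control. Under the combined definition its booster-phase AE proportion covers about twice the time and two vaccination visits, and its second month follows the vaccine under test. The proportion counts infants with at least one event, so a longer window can raise it but never lower it. Set beside Groups 1 and 2, the control would tend to look worse, and c7vPnC correspondingly better, even if AE risk per month were the same in all three groups.

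Under the split definition this imbalance of duration disappears. Two lines of the same SAP section support different tables, and the protocol supports the one that is not comparable. Both documents say that major modifications to primary endpoint definitions or their analysis will also appear in a protocol amendment (Protocol 9, SAP 2). The current protocol, Amendment 1, still has two intervals.

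**Working it through.** **1. The plan's own figure.** Protocol Table 5 gives the probability of at least one event with N = 188. The formula is 1 − (1 − p)^188:

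- p = 0.5%: 0.610 (stated 0.610)
- p = 1%: 0.849 (stated 0.849)
- p = 5%: 0.9999 (stated >0.999)

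All three reproduce. The table does not address window length; it supplies only the group size used below.

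**2. Length of the booster interval under each definition** (windows from Protocol 6.1.6, 6.2.10, 6.3.6 and 6.3.7).

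| | Combined (Protocol 2.1.2, 9.4; SAP 3.1; SAP 6.1.3.1 time points) | Split (SAP 6.1.3.1 endpoint line; SAP 4.1 populations) |
|---|---|---|
| Groups 1 and 2 | 28-42 days, one vaccination visit | 28-42 days, one vaccination visit |
| Group 3 | (28+28) to (42+42) = 56-84 days, two vaccination visits | 28-42 days after Dose 4; separately, 28-42 days after the Supplemental Dose |

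The ratio of the combined Group 3 interval to the interval in Groups 1 and 2 is 2.0 at matching positions in the windows. At the extremes it is 56/42 = 1.33 and 84/28 = 3.0.

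**3. Effect on the proportion.** The documents give no AE rates, so this is an illustration under assumptions. Let p be the one-month AE proportion, equal in all groups, with independent months. Group 3's combined proportion is then 1 − (1 − p)²:

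- p = 10%: 19%
- p = 20%: 36%
- p = 30%: 51%
- p = 40%: 64%

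For p = 20% with a constant event rate, the extremes of the windows give 1 − 0.8^1.33 = 26% and 1 − 0.8^3 = 49%.

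**4. Against sampling error.** With p = 20% and n = 188, the Clopper-Pearson 95% CIs are 14.7-26.7% (38/188) and 29.3-43.5% (68/188). They do not overlap, although the assumed risks are identical. The excess is 16 points. The approximate half-width for a difference is 1.96 × √(0.20×0.80/188 + 0.36×0.64/188) = 8.9 points.

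**5. Sensitivity to independence.** If the two months have correlation r within an infant, the probability of an event in both is p² + r·p(1 − p), so the excess is p(1 − p)(1 − r). With p = 20% and an assumed r = 0.5 it is 0.20 × 0.80 × 0.5 = 8 points (28% against 20%). The half-width for that difference is 1.96 × √(0.20×0.80/188 + 0.28×0.72/188) = 8.6 points. The excess reaches zero only at r = 1, when exactly the same infants have events in both months.

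**6. Sensitivity to group size.** 188 is the number randomized, and fewer will receive Dose 4. With the 160 per arm that Protocol 3.3 gives as evaluable for immunogenicity, used here only as a rough guide, the intervals for 20% and 36% are 14.1-27.0% (32/160) and 28.8-44.2% (58/160). They still do not overlap.

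**The case against.** The strongest reply is that the SAP already has the answer. Its endpoint line names three intervals, its population bullet names three matching populations, and SAP 4.1 stops Group 3's Dose 4 data at the Supplemental Dose. On that view one bullet and one copied endpoint have simply lagged behind. Much of this stands: the split is in the SAP, and the remedy is to bring the other passages into line with it. But the combined phrase is not a single slip. It is the protocol's rule in 2.1.2 and 9.4, and SAP 6.5.3 pairs the same combined interval with the Dose 4 safety population when summarizing concomitant vaccines and medications. The split cannot be taken as settled.

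A second reply is that the study is descriptive, with no tests and no decision rules (Protocol 9.1, SAP 5.1). That is right, and no error rate is affected. The proportions will still be tabulated with CIs by vaccine group, one of which is labelled the active control, to inform Phase 3 design. Readers will compare the columns.

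A third reply is that text is redacted near SAP 3.1, where the AE computation may have been described. Hidden text could settle which rule was programmed, so the effect on the reported table is not proven. It cannot remove the conflict between the visible lines.

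Three stronger readings go too far:

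- *The SAP ends the interval in three different ways.* For an infant on schedule there are two lengths. The one-month visit after Dose 4 and the Supplemental Dose are both Group 3 Visit 6, so the endpoint line and SAP 4.1 coincide. SAP 4.1 is also a population definition, not the endpoint interval. The two part only if the Supplemental Dose is delayed or not given.
- *Infants who never receive the Supplemental Dose are dropped from the Dose 4 population.* That is one reading of SAP 4.1. Its wording leaves the end of their period undefined but does not say they are excluded, and Protocol 6.5 keeps infants who stop vaccination in safety follow-up.
- *The control has two vaccinations against one.* Group 1 also receives two pneumococcal injections in its window, on one day (Protocol 6.1.5). The contrast is between two vaccination visits and one.

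**Conclusion.** The conflict is real and sits on a primary endpoint. Group 3's booster-phase AE proportion is either one figure over 56-84 days and two vaccination visits or two figures over 28-42 days each. The first is not comparable with Groups 1 and 2 on duration, and its longer window can only push the control figure up.

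The direction is certain if the combined rule is used; the size is not. A 16-point excess at a 20% monthly rate assumes equal risk and independent months. An assumed correlation of 0.5 halves it to 8 points, about the width of sampling error for a difference. A reader might infer that the reported control proportion will be inflated. The documents do not establish that, because the SAP also contains the split rule and some text is hidden. They establish that the protocol's own rule would have that effect and that the SAP does not clearly override it.

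This point concerns all AEs in the booster phase. It does not extend to the six-month SAE and NDCMC endpoint.

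**What to change.** 1. Make Protocol 2.1.2 and 9.4, SAP 3.1 and the SAP 6.1.3.1 time-points bullet match the endpoint line already in SAP 6.1.3.1, with three intervals: Dose 1 to one month after Dose 3; Dose 4 to one month after Dose 4 (in Group 3, up to the Supplemental Dose); and, for Group 3 only, the Supplemental Dose to one month after it.
2. Report the two Group 3 periods separately, and do not place a combined Group 3 proportion beside Groups 1 and 2.
3. Add a note that the split equalizes duration but not age or concomitant vaccines relative to Group 2. Group 2's Dose 4 is c7vPnC at 13 months without other injectable vaccines, whereas Group 3's is Prevnar 13 at 12 months with permitted vaccines.
4. In SAP 4.1, state that Group 3's Dose 4 period ends at the earlier of the Supplemental Dose and the one-month visit after Dose 4, and that receipt of the Supplemental Dose is not a condition for inclusion. Infants without it are then clearly kept.

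The cost is SAP wording and one protocol clarification. No new data are needed: AEs are collected through both periods and vaccination dates are recorded (Protocol 8.1.4 and 5.7.4).
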